10.3.5. Reporting of SAE to GSK

SAE Reporting to GSK via Electronic Data Collection Tool

• The primary mechanism for reporting SAE to GSK will be the electronic data collection tool.• If the electronic system is unavailable, then the site will use the paper SAE data collection tool (see next Section) to report the event within 24 hours.• The site will enter the SAE data into the electronic system as soon as it becomes available.• The investigator or medically qualified sub-investigator must show evidence within the eCRF (e.g., check review box, signature, etc.) of review and verification of the relationship of each SAE to IP/study participation (causality) within 72 hours of SAE entry into the eCRF.• After the study is completed at a given site, the electronic data collection tool will be taken off-line to prevent the entry of new data or changes to existing data.• If a site receives a report of a new SAE from a study participant or receives updated data on a previously reported SAE after the electronic data collection tool has been taken off-line, then the site can report this information on a paper SAE form (see next Section).• Contacts for SAE reporting can be found in the SRM and Investigator Site File.

SAE Reporting to GSK via Paper Data Collection Tool

• Facsimile transmission of the SAE paper data collection tool is the preferred method to transmit this information to the medical monitor or the SAE coordinator.• In rare circumstances and in the absence of facsimile equipment, notification by telephone is acceptable with a copy of the SAE data collection tool sent by overnight mail or courier service.• Initial notification via telephone does not replace the need for the investigator to complete and sign the SAE data collection tool within the designated reporting time frames.• Contacts for SAE reporting can be found in the SRM and Investigator Site File.

10.4. Appendix 4: Anaphylaxis Criteria

Joint NIAID/FAAN Second Symposium on Anaphylaxis [Sampson, 2006]. The criteria do not make a distinction based on underlying mechanism. These criteria are summarized as follows:

- 1) Acute onset of an illness (minutes to several hours) with involvement of the skin, mucosal tissue, or both (e.g., generalized hives, pruritus or flushing, swollen lips-tongue-uvula), and at least one of the following:
 - a) Respiratory compromise (e.g., dyspnoea, wheeze-bronchospasm, stridor, reduced peak expiratory flow [PEF], hypoxemia)
 - b) Reduced blood pressure (BP) or associated symptoms of end-organ dysfunction (e.g., hypotonia [collapse], syncope, incontinence)
- 2) Two or more of the following that occur rapidly after exposure to a likely allergen for that patient (minutes to several hours):
 - a) Involvement of the skin-mucosal tissue (e.g., generalized hives, itch-flush, swollen lips-tongue-uvula)
 - b) Respiratory compromise (e.g., dyspnoea, wheeze-bronchospasm, stridor, reduced PEF, hypoxemia)
 - c) Reduced BP or associated symptoms (e.g., hypotonia [collapse], syncope, incontinence)
 - d) Persistent gastrointestinal symptoms (e.g., crampy abdominal pain, vomiting)
- 3) Reduced BP after exposure to known allergen for that patient (minutes to several hours):
 - a) Infants and children: low systolic BP (age specific) or greater than 30% decrease in systolic BP
 - b) Adults: systolic BP of less than 90 mm Hg or greater than 30% decrease from that person's Baseline

10.5. Appendix 5: Contraceptive and Barrier Guidance

10.5.1. Definitions:

Woman of Childbearing Potential (WOCBP)

Women in the following categories are considered WOCBP (fertile):

1. Following menarche
2. From the time of menarche until becoming post-menopausal unless permanently sterile (see below)

Notes:

- A postmenopausal state is defined as no menses for 12 months without an alternative medical cause.
 - A high follicle-stimulating hormone (FSH) level in the postmenopausal range may be used to confirm a postmenopausal state in women not using hormonal contraception or hormonal replacement therapy (HRT). However, in the absence of 12 months of amenorrhea, confirmation with more than one FSH measurement is required.
 - Females on HRT and whose menopausal status is in doubt will be required to use one of the non-oestrogen hormonal highly effective contraception methods if they wish to continue their HRT during the study. Otherwise, they must discontinue HRT to allow confirmation of postmenopausal status before study enrolment.
- Permanent sterilization methods (for the purpose of this study) include:
 - Documented hysterectomy
 - Documented bilateral salpingectomy
 - Documented bilateral oophorectomy
- For individuals with permanent infertility due to an alternate medical cause other than the above, (e.g., Mullerian agenesis, androgen insensitivity, gonadal dysgenesis), investigator discretion should be applied to determining study entry.
- **Note:** Documentation can come from the site personnel's review of the participant's medical records, medical examination, or medical history interview.

If fertility is unclear (e.g., amenorrhea in adolescents or athletes) and a menstrual cycle cannot be confirmed before first dose of study intervention, additional evaluation should be considered.

10.5.2. Contraception Guidance

CONTRACEPTIVES ^a ALLOWED DURING THE STUDY INCLUDE:	
Highly Effective Methods ^b That Have Low User Dependency Failure rate of <1% per year when used consistently and correctly. 
 Implantable progestogen-only hormone contraception associated with inhibition of ovulation ^c Intrauterine device (IUD) Intrauterine hormone-releasing system (IUS) ^c Bilateral tubal occlusion Azoospermic partner (vasectomized or due to a medical cause) Azoospermia is a highly effective contraceptive method provided that the partner is the sole sexual partner of the woman of childbearing potential and the absence of sperm has been confirmed. If not, an additional highly effective method of contraception should be used. Spermatogenesis cycle is approximately 90 days. Note: documentation of azoospermia for a male participant can come from the site personnel's review of the participant's medical records, medical examination, or medical history interview.) 	
Highly Effective Methods ^b That Are User Dependent Failure rate of <1% per year when used consistently and correctly. 
 Combined (oestrogen- and progestogen-containing) hormonal contraception associated with inhibition of ovulation ^c 
 oral intravaginal transdermal injectable Progestogen-only hormone contraception associated with inhibition of ovulation ^c 
 oral injectable Sexual abstinence Sexual abstinence is considered a highly effective method only if defined as refraining from heterosexual intercourse during the entire period of risk associated with the study intervention. The reliability of sexual abstinence needs to be evaluated in relation to the duration of the study and the preferred and usual lifestyle of the participant. 	
Effective Methods ^d That Are Not Considered Highly Effective Failure rate of ≥ 1% per year when used consistently and correctly. 
 Progestogen-only oral hormonal contraception where inhibition of ovulation is not the primary mode of action Male or female condom with or without spermicide ^e Cervical cap, diaphragm, or sponge with spermicide A combination of male condom with either cervical cap, diaphragm, or sponge with spermicide (double-barrier methods) ^c 	

 Contraceptive use by men or women should be consistent with local regulations regarding the use of contraceptive methods for those participating in clinical studies. Failure rate of <1% per year when used consistently and correctly. Typical use failure rates differ from those when used consistently and correctly. Male condoms must be used in addition to hormonal contraception. If locally required, in accordance with Clinical Trial Facilitation Group (CTFG) guidelines, acceptable contraceptive methods are limited to those which inhibit ovulation as the primary mode of action. Considered effective, but not highly effective - failure rate of ≥1% per year. Periodic abstinence (calendar, sympto-thermal, post-ovulation methods), withdrawal (coitus interruptus), spermicides only, and lactational amenorrhea method (LAM) are not acceptable methods of contraception. Male condom and female condom should not be used together (due to risk of failure from friction). 	

10.6. Appendix 6: Genetics

USE/ANALYSIS OF DNA

- Genetic variation may impact a participant's response to study intervention, susceptibility, severity and progression of disease. Variable response to study intervention may be due to genetic determinants that impact drug absorption, distribution, metabolism, and excretion; mechanism of action of the drug; disease aetiology; and/or molecular subtype of the disease being treated. Therefore, where local regulations and IRB/IEC allow, a blood sample will be collected for DNA analysis
- DNA samples will be used for research related to mepolizumab or CRSwNP / ECRS and related diseases. They may also be used to develop tests/assays including diagnostic tests) related to mepolizumab or study interventions of this drug class, and indication. Genetic research may consist of the analysis of one or more candidate genes or the analysis of genetic markers throughout the genome or analysis of the entire genome (as appropriate).
- Additional analyses of DNA samples may be conducted if it is hypothesized that this may help further understand the clinical data.
- The samples may be analysed as part of a multi-study assessment of genetic factors involved in the response to mepolizumab or study interventions of this class. The results of genetic analyses may be reported in the clinical study report or in a separate study summary.
- The sponsor will store the DNA samples in a secure storage space with adequate measures to protect confidentiality.
- The samples will be retained while research on mepolizumab (or study interventions of this class) or nasal polyposis continues but no longer than 15 years after the last subject last visit or other period as per local requirements.

10.7. Appendix 7: Liver Safety: Required Actions, Monitoring and Follow-up Assessments

Liver Chemistry Stopping Criteria and Increased Monitoring Criteria are designed to assure participant safety and evaluate liver event aetiology.

Liver Chemistry Stopping Criteria and Required Follow-up Assessments

Liver Chemistry Stopping Criteria	
ALT-absolute	ALT \geq 8xULN
ALT Increase	ALT \geq 5xULN but <8 xULN persists for ≥ 2 weeks ALT \geq 3xULN but <5 xULN persists for ≥ 4 weeks
Bilirubin^{1, 2}	ALT \geq 3xULN and total bilirubin \geq 2xULN ($>35\%$ direct bilirubin)
INR²	ALT \geq 3xULN and INR >1.5
Cannot Monitor	ALT \geq 5xULN but <8 xULN and cannot be monitored weekly for ≥ 2 weeks ALT \geq 3xULN but <5 xULN and cannot be monitored weekly for ≥ 4 weeks
Symptomatic³	ALT \geq 3xULN associated with symptoms (new or worsening) believed to be related to liver injury or hypersensitivity
Required Actions, Monitoring and Follow-up Assessments	
Actions	Follow-Up Assessments

 Immediately discontinue study intervention Report the event to GSK within 24 hours Complete the liver event form and complete an SAE data collection tool if the event also meets the criteria for an SAE² Perform follow up assessments as described in the Follow-up Assessment column Monitor the participant until liver chemistries resolve, stabilize, or return to within baseline (see MONITORING below) 
MONITORING:
 
If ALT \geq 3xULN AND total bilirubin \geq 2xULN or INR >1.5:
	
 Viral hepatitis serology⁴ Obtain INR and recheck with each liver chemistry assessment until the aminotransferases values show downward trend Obtain blood sample for pharmacokinetic (PK) analysis within a week of meeting increased liver monitoring criteria⁵ Obtain a serum creatine phosphokinase (CPK), lactate dehydrogenase (LDH), gamma glutamyl transferase [GGT], glutamate dehydrogenase [GLDH], and serum albumin. Fractionate bilirubin, if total bilirubin \geq 2xULN


 Repeat liver chemistries (include ALT, AST, alkaline phosphatase, total bilirubin and INR) and perform liver event follow up assessments within 24 hours Monitor participant twice weekly until liver chemistries resolve, stabilize or return to within baseline A specialist or hepatology consultation is recommended 
For all other stopping criteria (total bilirubin $<2\times\text{ULN}$ and INR ≤ 1.5):
 
 Repeat liver chemistries (include ALT, AST, alkaline phosphatase, total bilirubin and INR) and perform liver event follow-up assessments within 24-72 hours Monitor participant weekly until liver chemistries resolve, stabilize or return to within baseline 
RESTART/RECHALLENGE
 
 Do not restart/rechallenge participant with study intervention since it is not allowed per protocol; continue participant in the study for any protocol specified follow-up assessments. 	
 Obtain complete blood count with differential to assess eosinophilia. Record the appearance or worsening of clinical symptoms of liver injury, or hypersensitivity, on liver event form Record use of concomitant medications on the concomitant medications report form including acetaminophen, herbal remedies, recreational drugs and other over the counter medications. Record alcohol use on the liver event alcohol intake form 
If $\text{ALT} \geq 3\times\text{ULN}$ AND total bilirubin $\geq 2\times\text{ULN}$ or INR > 1.5 obtain the following in addition to the assessments listed above:
 
 Anti-nuclear antibody, anti-smooth muscle antibody, Type 1 anti-liver kidney microsomal antibodies, and quantitative total immunoglobulin G (IgG) or gamma globulins. Serum acetaminophen adduct assay should be conducted (where available) to assess potential acetaminophen contribution to liver injury unless acetaminophen use is very unlikely in the preceding week. NOTE: not required in China Liver imaging (ultrasound, magnetic resonance, or computerised tomography) to evaluate liver disease: complete Liver Imaging form. Liver biopsy may be considered and discussed with local specialist if available, for instance: 
 In patients when serology raises the possibility of autoimmune hepatitis (AIH) In patients when suspected DILI progresses or fails to resolve on withdrawal of study intervention In patients with acute or chronic atypical presentation
---	---

	
• If liver biopsy conducted complete liver biopsy form
--	--

1. Serum bilirubin fractionation should be performed if testing is available. If serum bilirubin fractionation is not immediately available, discontinue study treatment for that participant if ALT \geq 3xULN and bilirubin \geq 2xULN. Additionally, if serum bilirubin fractionation testing is unavailable, **record presence of detectable urinary bilirubin on dipstick**, indicating direct bilirubin elevations and suggesting liver injury.
2. All events of ALT \geq 3xULN **and** bilirubin \geq 2xULN ($>35\%$ direct bilirubin) or ALT \geq 3xULN and INR >1.5 which may indicate severe liver injury (possible 'H's Law'), **must be reported to GSK as an SAE**; the INR threshold value stated will not apply to participants receiving anticoagulants.
3. New or worsening symptoms believed to be related to liver injury (such as fatigue, nausea, vomiting, right upper quadrant pain or tenderness, or jaundice) or believed to be related to hypersensitivity (such as fever, rash or eosinophilia).
4. Includes: Hepatitis A Immunoglobulin M (IgM) antibody; Hepatitis B surface antigen (HbsAg) and Hepatitis B Core Antibody (HBcAb); Hepatitis C RNA; Cytomegalovirus IgM antibody; Epstein-Barr viral capsid antigen IgM antibody (or if unavailable, heterophile antibody or monospot testing); and Hepatitis E IgM antibody. In those with underlying chronic hepatitis B at study entry (identified by positive hepatitis B surface antigen), quantitative hepatitis B DNA and hepatitis delta antibody. If hepatitis delta antibody assay cannot be performed, it can be replaced with a polymerase chain reaction (PCR) of hepatitis D RNA virus (where needed) [Le Gal, 2005].
5. Record the date/time of the PK blood sample draw and the date/time of the last dose of study intervention prior to PK blood sample draw on the CRF. If the date or time of the last dose is unclear, provide the participant's best approximation. If the date/time of the last dose cannot be approximated OR a PK sample cannot be collected in the time period indicated above, do not obtain a PK sample. Instructions for sample handling and shipping are in the SRM.

Liver Chemistry Increased Monitoring Criteria with Continued Study Intervention

Liver Chemistry Increased Monitoring Criteria and Actions with Continued Study Intervention	
Criteria	Actions

ALT \geq5xULN and $<$8xULN and total bilirubin $<$2xULN or INR\leq1.5 without symptoms believed to be related to liver injury or hypersensitivity, and who can be monitored weekly for 2 weeks.
 
OR
 
ALT \geq3xULN and $<$5xULN and total bilirubin $<$2xULN or INR\leq1.5 without symptoms believed to be related to liver injury or hypersensitivity, and who can be monitored weekly for 4 weeks.
	
 Notify the GSK Medical Monitor within 24 hours of learning of the abnormality to discuss participant safety. Participant can continue study treatment Participant must return weekly for repeat liver chemistries (ALT, AST, alkaline phosphatase, total bilirubin and INR) until they resolve, stabilise or return to within baseline. If at any time participant meets the liver chemistry stopping criteria, proceed as described above. If ALT decreases from ALT \geq5xULN and $<$8xULN to \geq3xULN but $<$5xULN (total bilirubin $<$2xULN and INR\leq1.5), continue to monitor liver chemistries weekly. If, after 4 weeks of monitoring, ALT $<$3xULN and bilirubin $<$2xULN and INR\leq1.5, monitor participants twice monthly until liver chemistries normalize or return to within baseline.

10.8. Appendix 8: AEs, ADEs, SAEs, SADEs, USADEs and Device Deficiencies: Definition and Procedures for Recording, Evaluating, Follow-up, and Reporting in Medical Device Studies

- The definitions and procedures detailed in this appendix are in accordance with ISO 14155 and European Medical Device Regulation (MDR) 2017/745 for clinical device research (if applicable).
- Both the investigator and the sponsor will comply with all local medical device reporting requirements for medical devices.
- The detection and documentation procedures described in this protocol apply to all GSK medical devices provided for use in the study (see Section 8.4.8. for the list of GSK medical devices).

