#### **4.5.3. Additional Safety Assessments**

##### **4.5.3.1. Laboratory Data**

Summaries of laboratory data including chemistry and haematology parameters, and liver function test data will be based on GSK Core Data Standards and unless otherwise specified will include on-treatment and post-treatment data. Change from baseline values for clinical chemistry and haematology will be summarised in separate tables using descriptive statistics.

Summaries of the number and percentage of participants with worst-case changes from baseline with respect to both the Normal Range (NR) and Potential Clinical Importance (PCI) criteria (for all lab tests where a PCI ranges are defined in the OPS) will be generated separately. Decreases to low, changes to normal or no changes from baseline,

and increases to high will be summarized for the worst-case post-baseline. If a participant has a decrease to low and an increase to high during the same time interval, then the participant is counted in both the “Decrease to Low” categories and the “Increase to High” categories. Participants with a missing baseline value are assumed to have been normal at baseline and participants with no data for a given lab test post-baseline (following first dose of study treatment) will be excluded from this summary.

Separate summary tables for haematology, and chemistry laboratory tests will be produced. These summaries will also be presented by Background INCS use subgroup (defined within Section 4.11.1).

Liver function laboratory tests will be included with chemistry lab tests.

Any liver stopping or liver monitoring events which occur during the study will be summarised. Summaries of hepatobiliary laboratory events including possible Hy’s law cases will also be provided in addition to what has been described above. Possible Hy’s law cases are defined as any elevated alanine aminotransferase (ALT)  $\geq 3 \times$  upper limit of normal (ULN), total bilirubin  $\geq 2 \times$  ULN and alkaline phosphatase (ALP)  $< 2 \times$  ULN/missing. Total bilirubin  $\geq 2 \times$  ULN can be within 28 days following the ALT elevation and if direct bilirubin is available on the same day, it must be  $\geq 35\%$  of total bilirubin.

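### Protocol Appendix 7: the criteria for continuing treatment under increased liver monitoring join the bilirubin and INR limits with *or*, so they overlap with two mandatory stopping criteria

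*Protocol*

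**What the plan says.** Protocol Appendix 7 (Section 10.7) has two tables.

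**Stopping table.** Two of its rows concern synthetic function or bilirubin. One is "ALT \geq 3xULN and total bilirubin \geq 2xULN", qualified by a direct fraction above 35%. The other is "ALT \geq 3xULN and INR >1.5". They are separate rows, so either is enough. The action is "Immediately discontinue study intervention".

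**Increased monitoring table.** The action here is "Participant can continue study treatment". There are two entry criteria:
- ALT from 5 to below 8×ULN, with "total bilirubin $<$2xULN or INR\leq1.5 without symptoms believed to be related to liver injury or hypersensitivity, and who can be monitored weekly for 2 weeks"
- ALT from 3 to below 5×ULN, with "total bilirubin $<$2xULN or INR\leq1.5 without symptoms believed to be related to liver injury or hypersensitivity, and who can be monitored weekly for 4 weeks"

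**The same pair of limits elsewhere in the appendix.** The stopping table's follow-up instructions for all remaining stopping criteria join bilirubin below 2×ULN and INR at or below 1.5 with *and*. The Actions column of the monitoring table does so twice. Only the two entry criteria use *or*: in both, the bilirubin limit is followed by "or INR\leq1.5 without symptoms believed to be related to liver injury or hypersensitivity".

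**Notes and cross-references.** A note to the bilirubin row requires stopping at the same ALT and bilirubin values when fractionation cannot be obtained at once. A note attached to the INR row exempts participants on anticoagulants from the INR threshold. The monitoring table's Actions column sends anyone who meets a stopping criterion at any time back to the stopping procedure.

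**The concern.** A list of who may continue and a list of who must stop should not share members. Here they do. A participant over one limit and under the other satisfies the *or* in the continue list and also meets a stopping row.

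These are not marginal laboratory values. Sections 10.2 and 10.3.2 and the Appendix 7 notes treat ALT at or above 3×ULN with either limit exceeded as a possible Hy's Law case to be reported as an SAE.

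The two tables also differ on follow-up for such a participant. The stopping table asks for repeat chemistry within 24 hours and monitoring twice a week, while the monitoring table asks for weekly repeats. Anyone who classifies from the criteria column, or programs an eCRF check or a data query from it, would get an answer that the stopping table contradicts.

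**Working it through.** There is no stated figure to reproduce; this is a check of logic.

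**Inputs, all from Appendix 7.** ALT band; bilirubin at or above 2×ULN or not; INR above 1.5 or not; symptoms present or not; weekly monitoring possible or not. Raised bilirubin is first taken to have a direct fraction above 35% (or no fractionation available), and raised INR to occur off anticoagulants. One time point is considered, so the persistence rows are not yet in play.

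**Step 1: the core comparison.** Take ALT from 3 to below 8×ULN, no symptoms, weekly monitoring possible.

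| Bilirubin | INR | Stopping table | Continue list with *or* (as written) | Continue list with *and* (as elsewhere in the appendix) |
|---|---|---|---|---|
| <2×ULN | ≤1.5 | no | yes | yes |
| ≥2×ULN | ≤1.5 | yes | **yes** | no |
| <2×ULN | >1.5 | yes | **yes** | no |
| ≥2×ULN | >1.5 | yes | no | no |

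The wording as written admits three of the four combinations. One of them, with both limits respected, causes no conflict. The other two are in both lists.

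Example: ALT 6×ULN, bilirubin 3×ULN with more than 35% direct, INR 1.2, no symptoms, weekly monitoring possible. This meets the bilirubin stopping row and the 5 to <8×ULN continue criterion. With normal bilirubin and INR 2.0, off anticoagulants, the INR stopping row and the same continue criterion are met.

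**Step 2: all states.** Three ALT bands (3 to <5, 5 to <8, ≥8×ULN) × 2 × 2 × 2 × 2 = 48 states. The number in both lists depends on how the criterion is read:
- *or* applied only between bilirubin and INR, the natural reading: 2 ALT bands × 2 mixed combinations = **4 of 48**.
- Strict operator precedence (*and* binding before *or*): **18 of 48**. The first clause, ALT in band with bilirubin <2×ULN, covers 2 × 2 × 2 × 2 = 16 states, of which 14 meet a stopping row. The second clause, INR ≤1.5 with no symptoms and feasible monitoring, adds 4 more, all meeting a stopping row. 14 + 4 = 18.
- *and*: **0 of 48**, with every state in exactly one list.

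These are counts of logical states, not probabilities.

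**Step 3: cases outside the step 1 assumptions.** Bilirubin at or above 2×ULN with a measured direct fraction of 35% or less meets no bilirubin stopping row. With INR ≤1.5, no symptoms and feasible monitoring, it is in the continue list under *or* and in neither list under *and*. An INR above 1.5 on anticoagulants, with bilirubin below 2×ULN and the other continue conditions met, behaves the same way if the exemption is applied to the stopping row. Neither case is an overlap, but changing the connective alone would leave both unassigned.

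**The case against.** The strongest reply is that the documents already give stopping priority. Protocol 7.1.2 makes discontinuation mandatory when any liver stopping criterion is met. Section 7.1.5 requires it for any condition in the stopping algorithm. The SAP's study design overview (1.2) repeats the obligation. The monitoring table has its own override line, and a permissive statement that treatment can continue does not outweigh these. A site would also have to overlook the 24-hour contact with the Medical Monitor and the SAE rule for the same values. In addition, the overlap is narrow. It does not arise on the natural reading when both limits are exceeded, when ALT is at or above 8×ULN, when symptoms are present, or when weekly monitoring is not possible. INR is not in the routine laboratory panel of Section 10.2.

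All of this stands, and it lowers the practical risk. It does not make the entry criteria consistent. The override sits in the Actions column, after the criteria column has already classed the participant as eligible to continue.

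Two stronger readings are tempting and should not be adopted. A reader might infer from SAP 4.5.3.1, "Any liver stopping or liver monitoring events which occur during the study will be summarised", that one episode would be counted twice. The sentence gives no derivation and no separate counts. Display and data-handling detail is deferred to the Output and Programming Specification. The associated listing takes participants meeting either set, so overlap does not change who is listed. Possible Hy's Law cases have their own SAP definition. A reader might also infer that Algorithms A and B carry the same fault. They are figures not shown in the text reviewed, so nothing can be said about them.

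**Conclusion.** The contradiction is real and limited. As written, a participant with ALT from 3 to below 8×ULN, no liver or hypersensitivity symptoms and feasible weekly monitoring, who exceeds exactly one of the two limits, meets both a mandatory stopping criterion and the criteria for continuing. On the natural reading this is two of four bilirubin-by-INR combinations, or 4 of 48 states. It rests on raised bilirubin being more than 35% direct or unfractionated, and on raised INR occurring off anticoagulants.

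This is an internal inconsistency in a safety rule. It is not a design choice, and it does not touch the efficacy endpoints, power or type I error. The mandatory wording elsewhere means that the documents do not support the inference that the plan instructs sites to keep dosing such participants. No view is taken here on which clinical rule is right.

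**What to change.** Reconcile the two entry criteria of the monitoring table with the stopping table, its follow-up instructions and the monitoring table's own Actions column, so that no participant meets both the stopping and the continue criteria. State explicitly where raised bilirubin with a direct fraction of 35% or less, and raised INR on anticoagulants, belong. Then check Algorithms A and B in Section 7.1.5 against the reconciled text.

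Requiring one connective throughout Appendix 7 would not work. A rule that stops on either of two limits is an *or*, and its complement is an *and*, so both words are needed in their places.

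The cost is a protocol wording correction and a letter to sites. No SAP text has to change. If the programming specification reproduces the protocol criteria, it should take the reconciled ones.
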